11.2. Adverse Drug Reaction (ADR)

All untoward and unintended responses to an investigational product related to any application/dose administered, i.e., having a reasonable causal relationship as judged by the Investigator. This means that there is evidence or argument to suggest a causal relationship.

11.3. Serious Adverse Event or Serious Adverse Reaction (SAE/SAR)

An adverse drug reaction is considered SERIOUS if it:

- Results in death
- Is life threatening

- Requires additional inpatient hospitalization or prolongation of existing hospitalization
- Results in persistent or significant disability / incapacity
- Results in a congenital anomaly or birth defect
- Other medically significant event that requires immediate medical or surgical intervention

An adverse drug reaction is considered UNEXPECTED if it:

Is not consistent with the Investigators' Brochure or SPC

CAUSAL RELATIONSHIP means:

- There are facts/evidence to suggest a causal relationship
- As judged by the reporting health care professional to have a reasonably suspected causal relationship

Expedited Reporting is required if all of the following criteria apply (ICH E2A):

- Serious
- Unexpected
- Causal relationship to study treatment

NOTE

Death: is the outcome of an adverse event. The event to be reported comprehensively is the medical condition leading to death, e.g., underlying disease or accident.

Life-threatening: in the definition of a serious adverse event or adverse reaction, "life-threatening" refers to an event in which the patient was at risk of death at the time of the event; it does not refer to an event that hypothetically might have caused death if it was more severe.

Medical judgment should be exercised in deciding whether an adverse event/reaction is serious in other situations. Important adverse events/reactions that are not immediately life-threatening or do not result in death or hospitalization but may jeopardize the patient or may require intervention to prevent one of the other outcomes listed in the definition above should also be considered serious.

11.4. Suspected Expected Serious Adverse Reaction (SESAR)

Any adverse reaction that is classified as serious in nature and that is consistent with the available information on the product in question according to:

a. In the case of a licensed product, the summary of product characteristics (SPC) for that product

b. In the case of any other investigational medicinal product, the Investigator's Brochure (IB) relating to the study in question

11.5. Suspected Unexpected Serious Adverse Reaction (SUSAR)

Any adverse reaction that is classified as serious in nature and that is **not** consistent with the available information on the medicinal product in question according to:

- a. In the case of a licensed product, the SPC for that product
- b. In the case of any other investigational medicinal product, the IB relating to the study in question.

11.6. Recording of Adverse Events

All adverse events, whether they are considered serious or not, will be documented and applicably reported according to previously provided definitions.

The investigator must report in detail all adverse signs and symptoms that are either volunteered by patients or observed during or following the course of Investigational Product administration on the appropriate CRF page.

Included in the description should be the nature of the sign or symptom; the date of onset; date of resolution (duration); the severity/intensity; the relationship to the study treatment or other therapy; the action taken (if any); and the outcome.

11.6.1. Definition of Adverse Event Intensity

Intensity	Definition
Mild	Patient is aware of signs and symptoms, but they are easily tolerated
Moderate	Signs/symptoms cause sufficient discomfort to interfere with usual activities
Severe	Patient is incapable to work or perform usual activities

11.6.2. Definition of Adverse Event causality

Based on the WHO-UMC system for standardized case causality assessment (www.who-umc.org), the following categories will be used to describe the degree of causality (all points should reasonably comply):

Definite

- Event or laboratory test abnormality, with plausible time relationship to drug intake
- Cannot be explained by disease or other drugs
- Response to withdrawal plausible (pharmacologically, pathologically)

- Event is definitive pharmacologically or phenomenologically (i.e., an objective and specific medical disorder or a recognized pharmacological phenomenon)
- Re-challenge satisfactory, if necessary

Probable

- Event or laboratory test abnormality, with reasonable time relationship to product intake
- Unlikely to be attributed to disease or other drugs
- Response to withdrawal clinically reasonable (for details refer to WHO-UMC)
- Re-challenge not required

Possible

- Event or laboratory test abnormality, with reasonable time relationship to drug intake
- Could also be explained by disease or other drugs
- Information on drug withdrawal may be lacking or unclear

Unlikely

- Event or laboratory test abnormality, with a time to drug intake that makes a relationship improbable (but not impossible)
- Disease or other drugs provide plausible explanations

Not related

The event does not follow a reasonable temporal sequence from administration of the IMP and is clearly related to other factors, such as clinical state, therapeutic intervention or concomitant therapy.

Not assessable

- Report suggesting an adverse reaction
- Cannot be judged because information is insufficient or contradictory
- Data cannot be supplemented or verified

All cases judged as having a "reasonable causal relationship" to the IMP qualify as ADR. This corresponds to the categories "definite," "probable" and "possible".

11.7. Reporting of Serious Adverse Events

All serious adverse reactions and all unexpected serious adverse reactions with at least a suspicion of a causal relationship to the investigational product must be reported to the manufacturer within 24 hours (one working day) of the Investigator first becoming aware.

Fatal or life-threatening SUSARs must be reported to the Ethics Committee and relevant regulatory bodies within 7 days; all other SUSARs must be reported within 15 days of knowledge if no other timelines are set out in the local drug law.

11.8. Adverse Event/Reaction follow-up procedures

Adverse events/reactions will be followed-up throughout the course of the clinical study.

12. STUDY SCHEDULE

12.1. Procedures at Each Visit

Visit 1: Screening/Baseline - 30-120 days from stroke onset

Patients will be informed about the study and an Informed consent will be obtained before any study-specific procedures will be carried out. Inclusion/exclusion criteria will be assessed and documented in the CRF. Patients who provide an informed consent and who meet all inclusion/exclusion criteria will be included in the study, and a randomization code will be assigned. After randomization, the medical history, vital signs, and patient demographic data as well as any concomitant medication will be measured or retrieved and recorded in the CRF. The baseline tests for all efficacy parameters (primary and secondary) will then be administered, and the results will be recorded in the CRF. Treatment with the study drug will be initiated with the first dose, and patients will receive the study drug for first 90 days of treatment.

Visit 2: 90 days from baseline

Vital signs will be taken, and changes in any of the concomitant medications will be recorded in the CRF. Any adverse events reported by the patient or noted by the investigator will be assessed and recorded in the CRF. Compliance with the study medication will be checked and recorded in the CRF. Tests for primary and secondary efficacy parameters will be administered and recorded. Patients will receive the study drug for the next 270 days of treatment.

VISIT 3: 360 days from baseline

Vital signs will be taken, and changes in any of the concomitant medications will be recorded in the CRF. Any adverse events reported by the patient or noted by the investigator will be assessed and recorded in the CRF. Compliance with the study medication will be checked and recorded in the CRF. Tests for primary and secondary efficacy parameters will be administered and recorded.

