5. STUDY DESIGN

Exploratory, prospective, randomized, open label, controlled study.

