7.4. Randomization, Blinding and Unblinding

8. PATIENTS WHO MEET THE INCLUSION AND EXCLUSION CRITERIA WILL BE RANDOMLY ASSIGNED TO THE TREATMENT GROUP OR CONTROL GROUP, IN A 2:1 RATIO. PATIENTS IN THE TREATMENT GROUP WILL RECEIVE ACTIVE DIET SUPPLEMENTATION MEANWHILE, THE PATIENTS IN THE CONTROL GROUP WILL NOT RECEIVE ANY KIND OF MEDICATION OR PLACEBO. INVESTIGATIONAL PRODUCTS

The regular marketable merchandise of N-Pep-12 (Cebrium) capsules will be obtained from pharmaceutical wholesalers in Romania.

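### Baseline efficacy tests come after randomisation in an open-label trial with an untreated control, so knowledge of the arm can influence the baseline; sign and size unknown

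*Protocol*

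**What the plan says.** Protocol section 12.1 sets out Visit 1 in order. Consent and eligibility come first. Eligible patients "will be included in the study, and a randomization code will be assigned". Next, "After randomization, the medical history, vital signs, and patient demographic data as well as any concomitant medication will be measured or retrieved". Then "The baseline tests for all efficacy parameters (primary and secondary) will then be administered". The last step is "Treatment with the study drug will be initiated with the first dose".

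Section 5 describes the trial as "Exploratory, prospective, randomized, open label, controlled study". Section 7.4 has patients "RANDOMLY ASSIGNED TO THE TREATMENT GROUP OR CONTROL GROUP, IN A 2:1 RATIO" and adds that "THE PATIENTS IN THE CONTROL GROUP WILL NOT RECEIVE ANY KIND OF MEDICATION OR PLACEBO". Its heading mentions blinding and unblinding, but its text describes no blinded assessor and no withholding of the assignment until testing is finished. The assessment table in section 12.2 has no row for randomisation, so it neither confirms nor changes the order in section 12.1.

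**The concern.** The baseline tests precede the first dose, so they are free of any product effect. They do not precede allocation, so they are not protected from what patient and rater know or expect. With no placebo, the arm is plain once it is disclosed.

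Two of the five primary scales look particularly open to this by the protocol's own description in section 10.1: PSI is said to depend partly on motivation, and HADS is the patient's own report of recent feelings. A rater who knows the arm could also affect the other performance tests. QEEG and eye-tracking recordings are probably less exposed.

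No earlier score can stand in. The eligibility criteria in sections 7.1 and 7.2 use a communication scale and the IQCODE but none of MoCA, HADS, CTT, DS or PSI. A baseline that the arm has influenced would carry part or all of that influence into any analysis that subtracts it or adjusts for it, and no later analysis choice can restore a clean one.

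**Working it through.** The protocol states no alpha, SD, correlation, effect size or analysis model, so there is no figure of its own to reproduce. The check has two parts: the order of procedures, and an illustration of what a shifted baseline would do.

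**Order.** Section 12.1 gives: consent, eligibility, code, history and vital signs, baseline tests, first dose. The wording is sequential at each step, and no other section reverses it or conceals the arm.

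**Inputs from the protocol (synopsis).** 60 patients in the intervention group and 30 in the reference group (60 + 30 = 90; 60/30 = 2).

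**Assumptions, not in the protocol.** No true effect; equal SDs, set to 1; two-sided alpha 0.05; correlation r = 0.6 between baseline and day 360; a between-arm shift s in the recorded baseline caused by knowledge of the arm.

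**Formulas (normal approximation).**
- f = √(1/60 + 1/30) = 0.2236.
- SE of the change-score difference = √(2(1 − r)) × f = √0.8 × 0.2236 = 0.200.
- SE of the ANCOVA difference = √(1 − r²) × f = 0.8 × 0.2236 = 0.179.
- Error rate = Φ(−1.96 − b/SE) + 1 − Φ(1.96 − b/SE), where b is the size of the bias.

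**Case A: baseline shifted, day 360 unaffected.** The size of the bias is s for a change score, r × s for ANCOVA, and 0 for an unadjusted day-360 comparison.
- s = 0.2, change score: b = 0.20, b/SE = 0.20/0.200 = 1.00, error about 17%.
- s = 0.2, ANCOVA: b = 0.6 × 0.2 = 0.12, b/SE = 0.12/0.179 = 0.67, error about 10%.

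The result depends on both assumed values:

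| r | s (SD) | Change-score bias; error | ANCOVA bias; error |
|---|---|---|---|
| 0.5 | 0.1 | 0.10; 7% | 0.05; 6% |
| 0.5 | 0.3 | 0.30; 27% | 0.15; 12% |
| 0.7 | 0.1 | 0.10; 9% | 0.07; 7% |
| 0.7 | 0.2 | 0.20; 21% | 0.14; 14% |
| 0.7 | 0.3 | 0.30; 41% | 0.21; 26% |
| 0.8 | 0.3 | 0.30; 56% | 0.24; 43% |

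A simulation of 4,000 trials at r = 0.7 and s = 0.3 gave a bias of 0.301 for the change score (rejection 41%), 0.209 for ANCOVA (24%) and −0.005 for the unadjusted comparison, in line with the formulas.

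**Case B: the same 0.2 SD shift also present at day 360 (r = 0.6).**
- Change score: 0.2 − 0.2 = 0.
- ANCOVA: (1 − 0.6) × 0.2 = 0.08, b/SE = 0.08/0.179 = 0.45, error about 7%.
- Unadjusted day-360 comparison: 0.20. This comes from the shift in the outcome itself, not from the baseline.

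**Direction.** Suppose controls, told that they will receive nothing, do worse at baseline by 0.2 SD and day 360 is unaffected. They then appear to improve more, which counts against the product. Of the 17% error on the change score, the part in favour of the product is 1 − Φ(1.96 + 1.00), about 0.15%, against a nominal 2.5%. For ANCOVA it is 1 − Φ(1.96 + 0.67), about 0.4%. A rater who favours the product could produce a shift in the opposite direction.

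**The case against.** The strongest case against concerns size and consequence, not the order, which is not in dispute.

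- **No baseline-adjusted analysis is named.** Section 13.1 gives no model, and any statistical analysis plan is not shown. This stands: the exposure applies only if the baseline is used.
- **The assumed shift has no source in the protocol, and Case A leaves day 360 untouched although it is also assessed open label.** This stands. Under Case B the change score removes the bias entirely, and using the baseline does better than ignoring it.
- **The direction is open.** This stands. A reader might take the 17% as a risk of false superiority, but under the discouraged-control mechanism nearly all of it falls on the control's side.
- **The study is exploratory.** The synopsis says it is not powered for any pre-defined statement. This lowers the severity but does not remove the point: section 4 still aims to show superiority, and the synopsis wants valid hypotheses for later studies.

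Two stronger readings are tempting. A reader might infer that these scores are not a valid baseline at all. The protocol does not support that: it does not say when patient or rater learns the arm after the code is assigned, and the tests precede dosing. A reader might also infer that controls are lost between randomisation and testing, leaving unequal groups at the start. Code, tests and first dose all belong to one visit, and nothing in the text indicates refusals between them.

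**Conclusion.** The point holds as an avoidable weakness in sequencing. Section 12.1 tests patients after allocation, the design makes the arm evident once it is disclosed, and the protocol offers no safeguard. It shows that the baseline can be influenced, not that it will be.

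Any resulting bias is of unknown sign and size. In the illustration with r = 0.6 and a 0.2 SD baseline shift, it ranges from 0 to 0.20 SD for a change score and from about 0.08 to 0.12 SD for ANCOVA, depending on whether the shift persists at day 360. These figures rest wholly on the assumed shift and correlation and are not estimates for this trial. Given the exploratory aim, this is a should-fix.

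**What to change.** Reorder Visit 1 in section 12.1: consent; eligibility; history, demographics, vital signs and concomitant medication; all five baseline scales and QEEG/eye tracking; then release of the randomisation code; then the first dose. State that no code is released until the baseline CRF pages are complete.

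This is a one-paragraph amendment using the same visit, tests and staff. The cost is that a few patients may be tested and then not randomised. For patients enrolled under the new order, allocation could no longer influence the baseline (s = 0), and this source of bias disappears. It does not remove open-label bias in the day-90 and day-360 assessments, which is a separate matter.

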10.1. Primary Variables

MoCA

Montreal Cognitive Assessment (MoCA) was designed as a rapid screening instrument for mild cognitive dysfunction. It assesses different cognitive domains: attention and concentration, executive functions, memory, language, visuo-constructional skills, conceptual thinking, calculations, and orientation. The time to administer the MoCA is approximately 10 minutes. The total possible score is 30 points; a score of 26 or above is considered normal.

• Processing Speed Index, Wechsler Adult Intelligence Scale, Fourth Edition

The Processing Speed Index (PSI) assesses skills such as focusing attention and quick scanning as well as discriminating between and sequentially ordering visual information. It requires persistence and planning ability, but it is sensitive to motivation, difficulty working under time pressure, and motor coordination as well. It is also related to reading, mathematical, and memory skills. Cultural factors seem to have little impact on processing speed. Processing Speed (PS) refers to the speed at which cognitive processes can be performed.

• Digit Span, Wechsler Adult Intelligence Scale, Fourth Edition

The Digit Span task exercises a patient's verbal working memory. Attention and comprehension also contribute to performance. The digit span task is a common component of many IQ tests, including the widely used WAIS (Wechsler Adult Intelligence Scales).

Performance on the digit span task is also closely linked to language learning abilities. The procedures for this assessment of working memory are considered standard. A list of numbers is read out loud at a rate of one number per second, and the participant is then asked to recall the numbers in order. The first list consists of three numbers and increases until the person begins to make errors. Lists with recognizable patterns (e.g., 1, 3, 5, 7, and 9) should be avoided, as people may remember these numbers more easily. At the end of each sequence, the participant is asked to the recall items in order. The average adult can remember a sequence of seven numbers, plus or minus two. This test can be distributed both backwards and forwards. Scores are thought to correlate with age and not intelligence.

Hospital Anxiety and Depression Scale

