12.2. Tabular Overview of Assessments

Visit 1 – Screening &	Visit 2 – Efficacy Evaluation	Visit 3 – Efficacy Evaluation
Baseline		primary endpoint
Informed Consent		
Inclusion Criteria		
Exclusion Criteria		
Patient Demographics		
Medical History	Changes in Medical History	Changes in Medical History
Concomitant Medication	Changes in Concomitant	Changes in Concomitant
	Medication	Medication
Vital Signs	Vital Signs	Vital Signs
Primary Efficacy Parameters	Primary Efficacy Parameters	Primary Efficacy Parameters
Adverse Events	Adverse Events	Adverse Events
	Compliance with Study Drug	Compliance with Study Drug
Subgroup analysis (QEEG,	Subgroup analysis (QEEG,	Subgroup analysis (QEEG,
ET)	ET)	ET)

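### No arm-masked assessment is specified for the tester-given primary scales or QEEG/eye-tracking processing, and sections 12.1 and 12.2 list testing and compliance checks in opposite orders

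*Protocol*

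**What the plan says.** - Section 5 describes the trial as "Exploratory, prospective, randomized, open label, controlled study".
- Section 7.4 is headed "Randomization, Blinding and Unblinding". The text that follows gives the 2:1 allocation and the control condition: "THE PATIENTS IN THE CONTROL GROUP WILL NOT RECEIVE ANY KIND OF MEDICATION OR PLACEBO". It says nothing about who is kept unaware of the arm.
- Section 12.1, Visits 2 and 3, lists vital signs and concomitant medication, then adverse events ("Any adverse events reported by the patient or noted by the investigator will be assessed and recorded in the CRF"), then compliance and the tests: "Compliance with the study medication will be checked and recorded in the CRF. Tests for primary and secondary efficacy parameters will be administered and recorded". The wording is the same at both visits.
- Section 12.2 tabulates the same visits with the primary efficacy parameters above adverse events and above the row "Compliance with Study Drug".
- Section 10.1 describes Digit Span as read aloud to the patient at a set pace, PSI as "sensitive to motivation, difficulty working under time pressure", and HADS as answered by the patient.

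No section says who gives or scores the tests, or who processes the QEEG and eye-tracking recordings.

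**The concern.** Open-label treatment does not require open-label measurement. Four of the five primary measures (MoCA, Digit Span, Color Trails, PSI) are performance tests given by a tester, so prompting, pacing, timing and scoring can be influenced by what that person expects. Controls receive nothing, so a question about compliance applies only to the treated arm. Asked before testing, it can show the arm to anyone present and remind the patient of it.

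Section 4 states a superiority aim for the 360-day outcome. If testers may know the arm, a modest difference could reflect their expectation as well as the product, and no analysis can separate the two once the data are collected. The trial's purpose, to generate valid hypotheses for later studies, depends on that separation.

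**Working it through.** The protocol states no figure on this point, so there is none to reproduce. The check is a reading of the sections against each other, followed by an illustration of scale.

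**1. Is anyone kept unaware of the arm?** Section 5 says open label, and 7.4 names blinding in its heading but provides none. Sections 10 and 12 do not mention the assessor's knowledge of allocation. Section 16.5 requires data to be stored under the patient's identifier, but this is a privacy measure. It masks the arm only if the allocation list is withheld from those who score and process.

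**2. What order is stated?**

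| Place | Order at Visits 2 and 3 | Sequence words |
|---|---|---|
| 12.1, visit text | adverse events, compliance, efficacy tests | none |
| 12.2, table | efficacy parameters, adverse events, compliance | none |

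Visit 1 differs. There the sequence is explicit: after randomization and the recording of history, "The baseline tests for all efficacy parameters (primary and secondary) will then be administered". The authors used sequence words where they meant a sequence, so the Visit 2 and 3 text reads as a list. The list and the table nevertheless run in opposite directions, and a site that works down 12.1 would test after the compliance check.

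**3. Which measures are exposed to the tester?** MoCA, Digit Span, Color Trails and PSI. The protocol describes administration in detail only for Digit Span; that the other three are also given by a tester follows from the kind of test they are. HADS is patient-answered, so its exposure comes from the patient knowing the arm. QEEG and eye tracking are instrument-recorded secondary measures, exposed mainly at processing.

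**4. Scale, for illustration only.**
- From the synopsis: 60 intervention and 30 reference patients.
- Assumed, not in the protocol: one endpoint, two-sided alpha of 5%, no true effect, normal approximation, and an assessment bias b in SD units favouring the intervention.
- SE of the difference = sqrt(1/60 + 1/30) = sqrt(0.05) = 0.2236 SD.
- False-positive rate = P(Z > 1.96 − b/SE) + P(Z < −1.96 − b/SE).
- b = 0.1: b/SE = 0.447, giving 0.0652 + 0.0080 = 7.3%.
- b = 0.2: b/SE = 0.894, giving 0.1433 + 0.0022 = 14.6% (0.1455 before rounding).
- If baseline adjustment is also assumed, with a correlation of 0.6, SE is multiplied by sqrt(1 − 0.36) = 0.8 and the rates become about 9% and 20%.
- For comparison, the smallest effect detectable at an assumed 80% power is 2.8 × 0.2236 = 0.63 SD unadjusted. A bias of 0.2 SD is about a third of that.

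**The case against.** A reader might infer from 12.1 that adverse events and compliance are always checked immediately before testing, and that the tester therefore knows the arm. The documents do not support this. The Visit 2 and 3 text has no sequence words, the table in 12.2 lists the items the other way round, and no section says that the person who tests also checks compliance or adverse events. This part of the objection stands: the tester may know the arm, and that is all that can be said.

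Order is also not the root cause. In an open-label trial a tester with access to allocation knows it whatever the order, and even the baseline tests follow randomization. This stands too, so the main point is the missing provision for masked assessment, and the ordering is secondary to it.

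The PSI description concerns the patient's motivation. Patients know their arm for 360 days, and neither masked testing nor reordering removes that. This stands as a limit on what the fix can achieve.

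Finally, the synopsis calls the analyses exploratory and not powered for pre-defined statements, so there is no stated confirmatory test whose error rate could be inflated. The percentages therefore only illustrate scale. This does not dispose of the point: biased measurement weakens an exploratory estimate as much as a confirmatory one, and who measures the primary endpoints, and what they know, is a matter of conduct that belongs in the protocol.

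**Conclusion.** The concern holds in this form: with open-label treatment and no placebo, the protocol specifies no arm-masked assessment of the four tester-given primary scales or of QEEG and eye-tracking processing, although 7.4 is headed as if it covered blinding. Sections 12.1 and 12.2 list testing and the compliance check in opposite orders and neither fixes a sequence, so the tester may know the arm.

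The documents do not show that any tester does know the arm, or that bias will occur, and its size cannot be derived from them. Under the assumptions stated (two-sided alpha of 5%, 60 versus 30, no true effect), a bias of 0.1 or 0.2 SD would give false-positive rates of about 7% or 15%. The point is worth acting on because the remedy is cheap and cannot be applied after data collection.

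**What to change.** 1. In 12.1, state that at Visits 2 and 3 the efficacy tests are done first, before the adverse event, concomitant medication and compliance checks, and bring 12.1 and 12.2 into agreement on this.
2. In 7.4, state that test sheets are scored and QEEG and eye-tracking files processed under the patient number, without the arm and without access to the allocation list.
3. Where existing staff allow, have the tests given by a team member who neither dispenses product nor checks compliance, and ask patients not to mention their group. The protocol gives no staffing for its single centre, so this step has to be conditional.

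Steps 1 and 2 need no extra staff, visit or procedure. The cost is somewhat less flexible scheduling. Some accidental unblinding will remain, and patient expectation, including its effect on HADS, is not removed and should be named as a limitation when results are reported.
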